Platelet-Rich Plasma Injection for the Treatment of Stress Urinary Incontinence in Females: A Randomized Placebo-Controlled Study

Specific aims

The primary aims of this randomized controlled trial study are to:

- 1. Evaluate the efficacy of platelet-rich plasma (PRP) injection into the anterior vaginal wall for the treatment of stress urinary incontinence (SUI) compared to placebo.
- 2. Evaluate the safety of PRP injection into the anterior vaginal wall for the treatment of SUI.

Hypothesis

Anterior vaginal wall PRP injection will be safe and associated with improved SUI compared to placebo.

Research Strategy

Significance and Innovation

Stress urinary incontinence (SUI), defined by the International Continence Society as the involuntary leakage of urine on effort or exertion, or on sneezing or coughing [1], is estimated to affect up to 49% of women [2, 3], many of whom undergo an operative intervention. Conservative management for SUI includes lifestyle interventions, pelvic floor muscle training, and incontinence pessaries. If conservative treatment fails or is not desired, surgical treatment via midurethral sling, colposuspension, pubovaginal sling, or bulking agent may be considered. Although surgery is highly effective in curing SUI, there are significant risks, such as hemorrhage, visceral injury, voiding dysfunction, chronic pain, and mesh exposure. Specifically, mid-urethral sling-related complications have been reported in up to 6% of patients [4] and include pain, exposure, erosion, dyspareunia, and long-term disability [5]. Complications after urethral bulking can include abscess formation, delayed hypersensitivity reactions, and vaginal erosion [6]. Fascial slings, compared to mid-urethral slings, have been shown to have a higher incidence of voiding dysfunction sometimes requiring intermittent catheterization, urethrolysis and/or prolonged suprapubic catheter use [7]. **Thus, there is an urgent need to evaluate innovative, minimally invasive, and low-risk procedures for SUI**.

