Treatment "success" will be defined as a negative CST and a reported PGI-I of "very much better" or "much better" 6 months after treatment.

The primary safety aim will be assessed by monitoring adverse events classified by the Clavien-Dindo Classification.

Secondary Outcomes that will be compared between groups include:

- 1. Female Sexual Function Index (FSFI) scores
- 2. Incontinence-Quality of Life (I-QOL) scores
- 3. Perception of Monetary Value
- 4. Questionnaire for Urinary Incontinence Diagnosis (QUID)
- 5. Visual Analog Scale (VAS) for patient pain/discomfort
- 6. Visual Analog Scale (VAS) for procedure difficulty (by provider)

Eligibility Criteria

- 1. Women aged 18 years or older
- 2. Pure or stress-predominant urinary incontinence with the Medical, Epidemiologic, and Social Aspects of Aging questionnaire (MESA) stress incontinence symptom score greater than MESA urge incontinence symptom score
- 3. Observation of leakage by provocative stress test at bladder volume \leq 300 mL [15]
- 4. Post void residual < 150 mL

Exclusion criteria

- 1. Currently pregnant or trying to conceive
- 2. Currently breastfeeding
- 3. Interstitial cystitis

- 4. Urgency urinary incontinence predominance or currently being treated for overactive bladder with medication, percutaneous tibial nerve stimulation, bladder chemodenervation, or sacral neuromodulation
- 5. Currently being treated for a sexually transmitted disease
- 6. Pelvic organ prolapse greater than stage 2 according to the Pelvic Organ Prolapse Quantification System
- 7. Periurethral mass
- 8. Active gynecologic, urologic or colorectal cancer
- 9. Any history of cancer within the last 5 years
- 10. Mental disorder making the patient unable to provide consent
- 11. Undiagnosed abnormal uterine bleeding
- 12. Genitourinary fistula
- 13. Prior SUI surgery
- 14. Use of anti-platelet or anti-coagulant medication
- 15. Use of non-steroidal anti-inflammatories
- 16. Regular use of non-steroidal anti-inflammatories

Methodology

This is a single-blind prospective randomized controlled trial comparing the efficacy of injection of 5 mL PRP into the anterior vaginal wall versus injection of 5 mL injectable saline for the treatment of SUI in females.

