Randomization will be performed with the help of a biostatistician. Participants will be block randomized with equal allocation to the treatment and control groups. To develop the assignment table, blocks of size 2, 4, or 6 participants were randomly selected until we achieved the anticipated sample of 50. Within each block, half of participants will be randomly assigned to one group and half to the other, ensuring equal treatment allocation. The randomization schedule will be transferred to sequentially numbered, opaque, sealed envelopes.

The principal investigator and the research coordinator will be responsible for maintaining the confidentiality and security of the randomization.

At this point, the clinical research coordinator will then open the randomization envelope. Randomization will be performed as described. The subject's initials and the date of injection will be written on the outside of the envelope prior to the envelope being opened. This writing will be transferred to the card containing the assigned randomization inside the envelope with carbon transfer paper. If the subject is assigned the active treatment, the sample will be used. If the subject is assigned the placebo, the sample will be discarded appropriately.

Injection Procedure

The injection procedure will be performed using previously published methods. The PI and 1 co-investigator will perform the procedure to ensure it is done in a standardized and reproducible method throughout the trial.

The injector will enter the clinic room with the patient already in the dorsal lithotomy position. A local anesthetic of lidocaine gel 2% will have been applied to the distal anterior vaginal wall 20 minutes before injections. The injector will then inject 5 mL total of either the active PRP or the placebo based on

randomization. The PRP will be injected into 3 sites of the anterior vaginal mucosa at the mid-urethra (about 1 cm proximal to the urethral meatus) using a 30-gauge needle. *Figure 1* diagrams the location and depth of the injections. The location of the injections is based on a pilot study by Long *et al* [12]. Immediately after the procedure, the patient will be given the VAS for pain/discomfort related to the procedure and the injector will complete the VAS for procedure difficulty.

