At baseline and at time points of 1 month, 3 months, and 6 months, subjects will complete the previously described validated questionnaires (see visit details below). At a 1-month telephone visit, a subset of the questionnaires will be administered, and patients will be queried about any adverse events. At baseline and at time points of 3 and 6 months, all validated questionnaires will be completed, as well as a pelvic exam with a urinary stress test, performed by a nurse practitioner specifically trained in urogynecology, and who did not perform the injections and thus blinded to the randomization. All adverse events will be recorded and classified per the Clavien-Dindo Classification.

Figure 1. Location and Depth of Injections¹²

At the end of the 6 months, subjects will be unblinded.

If subjects have symptoms of SUI which are refractory to treatment with PRP they will be referred to Urology or Urogynecology and will be offered standard of care following completion of the final study visit. If patients wish to receive alternative treatment for SUI prior to completion of 6-month follow-up they will be exited from the trial and final outcomes will be assessed at that time

Subjects will be provided a \$50 eVoucher upon completion of the 6-month follow-up visit.

Data will be stored in a secure REDCap database, only accessible to the research team members. Randomization envelopes and the Randomization Log will be kept in a locked cabinet.

Power Analysis

Sample size calculations were performed based on a desired power of at least 90% and assuming true response rates of 70% and 20% for treatment and placebo groups, respectively. The 70% response rate in the active PRP treatment group was chosen based on prior studies of PRP, as well as urethral bulking procedures [12] [16] [17]. The response rate of 20% in the placebo arm was chosen based on prior urethral bulking studies showing a 20% rate of negative CST after placebo [18]. Using an unadjusted alpha of 0.05, a sample of 38 subjects (19 per treatment group) is the minimum number required to have >90% power to detect a difference between the response rates of the two treatments.

In order to account for a 20% drop-out rate, we will plan to enroll a total of 50 patients (25 per treatment group).

Statistical Analysis and Data Reporting

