For this study we will assess the demographics of our patients by providing summary statistics stratified by treatment group. Comparisons between the demographics of the two treatment groups will be made using Fisher's Exact or chi squared tests for categorical variables and using T-test or Wilcoxon rank sum tests for continuous variables, where appropriate. Primary and secondary outcomes will also be compared using treatment-stratified summary statistics, and p-values obtained using the aforementioned statistical tests.

Univariate logistic regression models will be fit using the demographic variables obtained in the study, as well as treatment, to predict patients' primary outcomes. Then, one multivariate model will be constructed for each primary outcome with treatment included as a predictor and an AIC-based stepwise forward model selection procedure dictating what other variables to include into the model. Univariate generalized linear models using treatment group as the predictor variable will also be examined for the secondary outcomes.

Data will be reported using the CONsolidated Standards Of Reporting Trials (CONSORT) guidelines and standard flow diagram.

Breaking the Blind

A subject's treatment assignment will not be broken until the end of the study unless medical treatment of the subject is dependent on knowing the treatment the subject received. Should a medical emergency require the blind to be broken the investigator may unblind an individual subject's treatment allocation.

Research Visit Summary:

Baseline visit confirming eligibility with inclusion and exclusion criteria

Basic demographic data will be recorded

Past medical history will be recorded

Pregnancy test (if of child-bearing age)

Urinalysis dipstick to exclude active urinary tract infection

Bladder scan to see how much urine is in the bladder prior to urinary stress test

Pelvic exam with urinary stress test

Bladder scan after voiding to check post-void residual

Three surveys before the procedure

- Female Sexual Function Index
- Incontinence Quality of Life
- Questionnaire for Urinary Incontinence Diagnosis

Blood draw of about 15 mL

Randomization

Injection procedure

Visual analog Scale (VAS) for pain/discomfort associated with the procedure Injector completes Visual analog Scale (VAS) for level of difficulty of procedure

1-Month Telephone Visit

Record any adverse events

Surveys

- Incontinence Quality of Life

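### The primary safety aim has no criterion and no planned interval, and a non-significant comparison with a saline injection cannot support a claim that the injection is safe

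*Combined protocol and SAP*

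**What the plan says.** The Specific aims list efficacy and safety as the two primary aims. The Hypothesis section reads "Anterior vaginal wall PRP injection will be safe and associated with improved SUI compared to placebo". Under Approach, "The primary safety aim will be assessed by monitoring adverse events classified by the Clavien-Dindo Classification". No acceptable rate, grade threshold, margin or interval is attached to that aim.

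The control is an active injection procedure. Methodology describes "injection of 5 mL PRP into the anterior vaginal wall versus injection of 5 mL injectable saline", given by the same two injectors. The three injection sites are written out for PRP only, but the same route for saline is strongly implied.

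Statistical Analysis and Data Reporting has no separate safety paragraph. It names Fisher's "Exact or chi squared tests for categorical variables", to be used as suitable, and continues: "Primary and secondary outcomes will also be compared using treatment-stratified summary statistics, and p-values obtained using the aforementioned statistical tests". It then adds logistic models for the primary outcomes with treatment as a predictor, which is again a between-arm contrast. The Power Analysis covers efficacy only. The halting provision in Benchmarks for Success is qualitative and carries no number.

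**The concern.** A hypothesis that an injection will be safe is a statement about the size of a risk. The inference on offer asks a different question: whether PRP differs from saline.

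- **Contrast.** Harm caused by the injection itself can occur in both arms and drops out of the difference, although the aim concerns the safety of the injection.
- **Direction.** The tests look for a difference. In a small trial, not finding one is the likely result over a wide range of true risks, so it carries little information about safety.

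At stake is the conclusion on a primary aim. Nothing in the plan says how the adverse event results are to be turned into a statement about safety, and nothing prevents a non-significant p-value from being used for that purpose.

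**Working it through.** **Inputs from the document.** 25 women per arm enrolled, 1:1 allocation, 20% drop-out (so about 20 per arm), and "Using an unadjusted alpha of 0.05" (Power Analysis). Sidedness is not stated; two-sided is assumed.

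**Assumptions.** The document gives no adverse event rates. The true rates below are illustrative and shown over a range.

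**1. The plan's own figure (efficacy).** With rates 0.70 and 0.20 and mean 0.45:

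n = [1.960·√(2·0.45·0.55) + 1.282·√(0.70·0.30 + 0.20·0.80)]² / 0.50² = [1.379 + 0.780]² / 0.25 ≈ 18.6, so 19 per arm.

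This reproduces the stated 38 and supports the two-sided reading. Drop-out: 38/0.8 = 47.5, so 48, close to the planned 50. The document gives no corresponding safety calculation.

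**2. Harm common to both arms.** 10/25 versus 10/25 gives Fisher p = 1.0, while the PRP-arm rate is 40% (exact 95% interval 21% to 61%).

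**3. What the named tests flag when saline has no events.** Two-sided p-values for k/25 versus 0/25:

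| k | Fisher | Uncorrected chi-squared |
|---|---|---|
| 3 | 0.235 | 0.074 |
| 4 | 0.110 | 0.037 |
| 5 | 0.0502 | 0.018 |
| 6 | 0.022 | 0.009 |

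As a check for k = 3: Fisher is 2·C(25,3)/C(50,3) = 2·2300/19600 = 0.235. Chi-squared is 50·(3·25)²/(25·25·3·47) = 3.19, p = 0.074.

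**4. Power at 25 per arm.** With no saline events, Fisher needs at least 6 PRP events and uncorrected chi-squared at least 4. Power is then P(X ≥ 6) or P(X ≥ 4) for X ~ Binomial(25, p). For a non-zero saline rate, all pairs of outcomes were enumerated.

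| Assumed true rates, PRP vs saline | Fisher | Chi-squared |
|---|---|---|
| 10% vs 0% | 3% | 24% |
| 15% vs 5% | 7% | 21% |
| 20% vs 5% | 20% | 38% |
| 20% vs 0% | 38% | 77% |

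With 20 per arm, 10% vs 0% gives 4% and 13%.

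**5. What zero events would show.** The exact two-sided 95% upper limit for 0/n is 1 − 0.025^(1/n):

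- n = 25: 13.7%
- n = 20: 16.8%
- n = 50 (both arms pooled): 7.1%

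**The case against.** Several points on the other side stand.

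- **The p-value is not the whole plan.** Summaries by arm are promised in the same sentence, all adverse events are recorded and graded by Clavien-Dindo, and procedural pain is measured by VAS. Injection harms stay visible descriptively; they cancel only in the between-arm comparison. What is missing is an interval, a pooled rate and a rule for interpretation.
- **The analysis sentence does not name adverse events.** Applying it to a stated primary aim is the natural reading but not the only one. On the other reading, a primary aim has no inferential analysis at all, and the same fix is needed.
- **The PRP-versus-saline contrast is legitimate.** It isolates harm attributable to PRP. It is incomplete for procedural harm, but not wrong in itself.

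A reader might also infer three stronger claims that the document does not support.

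- **That the test could not flag 5/25 versus 0/25.** Fisher just misses (p = 0.0502), but uncorrected chi-squared, also named, gives 0.018, and Fisher flags 5/20 versus 0/20 (p = 0.047). Expected event counts of 2.5 per arm make Fisher the conventional choice, but the plan does not fix it. The example 3/25 versus 0/25 does not depend on that choice.
- **That a non-significant result will be called safe.** No section says so.
- **That the trial has set itself a 6% limit.** Significance and Innovation says "mid-urethral sling-related complications have been reported in up to 6% of patients", but as background on slings. The plan proposes neither a target rate nor a comparison with surgery.

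**Conclusion.** The point holds as a gap between the safety hypothesis and the inference planned for it. No criterion or interval is given, and on the natural reading the only inference is a comparison with another injection. That comparison is blind to shared harm and has low power: 3% or 24% at an assumed 10% versus 0%, depending on the test. The power figures rest on assumed event rates and a two-sided 0.05 level. The upper limits for zero events (13.7%, 16.8% and 7.1%) depend only on the numbers of women.

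It does not follow that the adverse event data are inadequate, that the p-value must be removed, or that the authors intend to misreport. Data collection and the efficacy analysis are unaffected. This is a cheap improvement.

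**What to change.** In Specific aims and Hypothesis, state the safety aim as estimation of adverse event rates and align the wording of the hypothesis. In Statistical Analysis and Data Reporting, add a short safety paragraph:

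- Report the number and proportion of women with any adverse event, and by Clavien-Dindo grade, with exact (Clopper-Pearson) 95% intervals, for each arm and for all injected women pooled. The pooled row addresses harms of the procedure; the PRP row remains the estimate for PRP.
- Report the PRP-minus-saline difference with a 95% interval, for example Newcombe's. With 0/25 in both arms this runs from −13.3 to +13.3 percentage points.
- Treat any p-value for adverse events as supplementary, and name the test in advance, because Fisher and uncorrected chi-squared can disagree at these counts.
- State that a non-significant difference, or zero events, will not be reported as showing safety.

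The cost is a few sentences, with no new data, visits or participants. The downside is a more modest safety claim.

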Platelet-rich plasma (PRP) is an autologous solution of human plasma with a high concentration of platelets. Platelet-rich plasma contains various growth factors that enhance the healing process and regeneration by initiating the stages of cell proliferation, differentiation, angiogenesis, and chemotaxis. The rationale for use and therapeutic potential of a high concentration of platelets is based on their capacity to supply supraphysiologic amounts of essential growth factors and cytokines which then provide a regenerative stimulus, promoting tissue repair [8]. Important growth factors released from platelets during the healing process include platelet-derived growth factor (PDGF), transforming growth factor (TGF- β), vascular endothelial growth factor (VEGF), epidermal growth factor (EGF), basic fibroblast growth factor (bFGF), and insulin-like growth factor (IGF-1) [9].

PRP has been described for the treatment of various health conditions, from hair loss to joint injuries. PRP is most studied and used for the treatment of musculoskeletal soft tissue injuries, including tendinopathies and tendon tears, and ligament, muscle, and cartilage injuries [10]. The injection of PRP is not a new technology, but it has not been well-studied in the field of urogynecology. Two small series have reported on use of PRP

for the treatment of female SUI, suggesting successful treatment outcomes in up to 80% of patients [11] [12]. With this study, we will provide higher quality evidence on the use of PRP in the treatment of SUI.

This study will aim to determine the 6-month post-treatment efficacy of PRP injection in the treatment of **SUI.** Knowledge gained from this study has the power to change clinical practice by equipping physicians with a minimally invasive and likely low risk SUI treatment.

Approach

The primary aims of this study are to determine the efficacy and safety of PRP injection into the anterior vaginal wall for the treatment of SUI.

The primary efficacy aim will be determined by the following outcome measures:

- 1. Negative urinary stress test (no leakage noted on examination during cough or Valsalva maneuvers at a standardized bladder volume of 300 mL [13]
- 2. Subjective outcome with improvement in the Patient Global Impression of Improvement (PGI-I), with positive response defined as "very much better" (1) or "much better" (2). [14]

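### A forward-AIC logistic model could supply the treatment effect in about 40 women, and the plan names no single confirmatory endpoint or test

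*Combined protocol and SAP*

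**What the plan says.** **Endpoint.** Significance and Innovation gives the aim: "This study will aim to determine the 6-month post-treatment efficacy of PRP injection in the treatment of" SUI. Approach then says "The primary efficacy aim will be determined by the following outcome measures" and lists two, a negative stress test and a PGI-I response, neither with its own time point. It goes on to define treatment success, which "will be defined as a negative CST and a reported PGI-I of" 1 or 2, at 6 months. That composite matches the stated aim, but the word primary is not attached to it. Safety has a primary aim of its own: "The primary safety aim will be assessed by monitoring adverse events classified by the Clavien-Dindo Classification".

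**Analysis.** Statistical Analysis and Data Reporting plans three things for the primary outcomes:

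- Unadjusted tests: "Primary and secondary outcomes will also be compared using treatment-stratified summary statistics, and p-values obtained using the aforementioned statistical tests". For categorical data these are Fisher's exact or chi-squared, with no written rule for choosing.
- Single-predictor models: "Univariate logistic regression models will be fit using the demographic variables obtained in the study, as well as treatment".
- A multivariable model: "one multivariate model will be constructed for each primary outcome with treatment included as a predictor and an AIC-based stepwise forward model selection procedure" then decides the other terms.

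The candidate pool is described only as demographic variables. The Research Visit Summary does not list them.

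**Size.** Power Analysis states that "a sample of 38 subjects (19 per treatment group) is the minimum number required to have >90% power", for response rates of 70% and 20% at alpha 0.05. It plans 50 enrolled, and the Timetable counts 40 of these as evaluable.

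**The concern.** There are two linked problems.

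1. Forward AIC chooses covariates from the same outcome data that the model then uses to estimate treatment. In a sample this small, chance-selected covariates overfit. A real treatment effect is then pushed further from an odds ratio of 1, and the more candidates there are, the further it moves. Likelihood-ratio tests become too liberal. Nothing in the plan marks this model as supportive.

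2. No endpoint and analysis are designated as deciding the trial. The plural in *each primary outcome* may mean efficacy plus safety, or the stress test and PGI-I separately; the text does not say. Even if the composite alone is meant, a positive claim could rest on the unadjusted p-value or on the model p-value, and the published odds ratio could be the exaggerated one.

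Timing adds to this. Under Benchmarks for Success, research-team members acting as the monitoring board analyse preliminary data at 25 subjects. People who will have seen data would then still have the choice of endpoint, test and model open to them.

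**Working it through.** **Inputs from the documents:** rates 0.70 and 0.20; alpha 0.05 (two-sided reproduces the stated size); power at least 90%; 1:1 allocation; 40 evaluable women. **Assumed:** 3, 5 or 10 candidate covariates, because the plan gives no number; all are pure noise, half normal and half binary.

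**1. The plan's own figure.** With pooled rate (0.70 + 0.20)/2 = 0.45,

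n = [1.960·√(2·0.45·0.55) + 1.282·√(0.70·0.30 + 0.20·0.80)]² / 0.50² = (1.379 + 0.780)² / 0.25 = 18.6,

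so 19 per arm and 38 in total. This reproduces.

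**2. Exact power at 19 per arm.** Summing the binomial probabilities of all significant tables gives:

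- chi-squared without continuity correction: 90.74%
- chi-squared, with Fisher if any expected count is below 5: 90.73% (Fisher is called for in 0.18% of trials)
- Fisher throughout: 85.2%

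The power claim therefore holds unless Fisher is used throughout.

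**3. Information available.** Expected successes are 20·0.70 + 20·0.20 = 18 of 40. The true odds ratio is (0.70/0.30)/(0.20/0.80) = 9.3.

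**4. How often noise enters.** AIC adds a term when twice the log-likelihood gain exceeds 2. For one noise covariate the large-sample chance is P(χ²₁ > 2) = 0.157. At least one of k enters with probability about 1 − 0.843^k: 40%, 57% and 82% for k = 3, 5 and 10. Simulation at n = 40 gives somewhat more (next table).

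**5. Treatment odds ratio at 70% v 20%, 20 per arm, treatment forced in**

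| | 3 candidates | 5 | 10 |
|---|---|---|---|
| At least one noise covariate picked | 47% | 63% | 86% |
| Median OR, AIC model | 12.0 | 13.2 | 20.3 |
| Median OR, same number of covariates fixed in advance | 10.5 | 10.9 | 12.3 |
| Ratio of the two (selection part) | 1.1 | 1.2 | 1.7 |
| OR above twice the truth, AIC | 31% | 36% | 52% |
| OR above twice the truth, fixed in advance | 24% | 27% | 33% |
| Wald power, AIC model | 88.1% | 88.4% | 82.5% |
| Unadjusted test, same replicates | 90.1% | 91.5% | 90.8% |

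For reference, the unadjusted median is 10.5 and one fixed covariate gives 10.9–11.5. Wald 95% interval coverage for the AIC model is 96–98%. These are 4,000 replicates per setting, or 2,000–3,000 for the comparison with fixed covariates and for coverage. A separate simulation with 4, 6 and 8 candidates gave medians of 12.8, 14.9 and 16.4, in line with the table.

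**6. Error with no treatment effect**

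| | 3 | 5 | 10 |
|---|---|---|---|
| AIC, likelihood-ratio test, 20% rate | 7.3% | 9.3% | 18.1% |
| AIC, likelihood-ratio test, 45% rate | 6.1% | 7.0% | 11.1% |
| AIC, Wald test, 20% rate | 3.0% | 3.8% | 4.9% |
| AIC, Wald test, 45% rate | 5.2% | 6.0% | 8.0% |
| Better of unadjusted test or AIC Wald, 20% rate | 4.2% | 5.0% | 6.0% |
| Better of unadjusted test or AIC Wald, 45% rate | 5.7% | 6.5% | 8.7% |

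The unadjusted test here uses the expected-count rule. Enumerated as in step 2 at 20 per arm, that test alone has size 3.3% at a 20% rate and 4.4% at 45%. A likelihood-ratio test with one fixed covariate errs in 5.5–6.9%.

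**7. Worst reading, which the plan does not state.** If a win on any of stress test, PGI-I or composite counted, unadjusted tests would err in 6.4–10.6% (expected-count rule), 10.1–12.5% (chi-squared throughout) or 4.5–5.9% (Fisher throughout). This covers null rates of 20–45% and latent correlations of 0–0.7.

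**The case against.** The strongest reply is that the sound analysis is already planned. The unadjusted comparison comes first, the sample size is built on it, and the regression follows as a prediction exercise; nothing says the AIC model supplies the treatment effect. The composite sits directly after the two measures and has the right time point, and two primary aims explain the plural. At the protocol's 20% placebo rate, picking the better of two analyses errs in only 4.2–6.0%. The large figures need 10 candidates, a 45% null rate or a likelihood-ratio test that the plan does not name. Interval coverage is unharmed, and with no true effect the median odds ratio stays at about 1.

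Much of this stands. The any-outcome reading is not the plan's, Wald inference is only mildly affected, and with 3 or 5 candidates the selection part is modest. The simulation also covers noise covariates only. If some candidates are prognostic, the adjusted odds ratio becomes a conditional quantity that depends on which covariates were picked, so it is no easier to interpret.

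The reply does not remove the gap. The unadjusted test is not designated as confirmatory, the model contains treatment and is not labelled exploratory, and even 3 candidates move the median odds ratio to 12.0.

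**Conclusion.** The concern holds and should be fixed. The textual part is certain: the composite is never called primary, no analysis is named as confirmatory, and the AIC candidates are not listed. The size of the statistical part depends on an assumed number of candidates. From 3 to 10 noise covariates, the median treatment odds ratio is 12.0 to 20.3 against a true 9.3, of which selection accounts for about 1.1- to 1.7-fold; the rest is ordinary small-sample bias. Null error is a real problem for a likelihood-ratio test and small for a Wald test. A single unadjusted test in this randomised trial is sound, and the stated 38 subjects with more than 90% power is correct provided that Fisher's test is not used throughout.

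**What to change.** Replace the analysis wording along these lines:

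- The sole primary efficacy endpoint is treatment success (negative stress test and PGI-I of 1 or 2) at 6 months. The stress test and PGI-I taken separately are secondary.
- The sole confirmatory efficacy analysis is one two-sided test of the two success proportions at 0.05: Pearson chi-squared without continuity correction, or Fisher's exact test if any expected count is below 5. Report the risk difference with its 95% confidence interval. Chi-squared throughout is also acceptable if written down.
- One supportive logistic model contains treatment and one baseline covariate, fixed before the 25-subject review and before any participant is unblinded. Baseline QUID is one example and is already collected.
- Any stepwise model is exploratory, with its candidates listed; its treatment odds ratio and p-value are not reported as efficacy results.

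The cost is wording only, with no new data, visits or subjects. There are four downsides:

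- The two component measures lose any separate primary status.
- Data-driven adjustment is given up.
- One fixed covariate still leaves a median odds ratio of about 11 against 9.3, so the risk difference should lead.
- The test's own size can exceed 5% under either rule, reaching about 5.8% at 19 per arm and 6.5% at 25 per arm over null rates of 10–50%.

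### FSFI, I-QOL and QUID are scored before randomization, but their planned comparisons ignore the baseline score and do not name the response; adjusting for baseline would usually be more precise at no data cost

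*Combined protocol and SAP*

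**What the plan says.** The Approach section introduces six outcomes with "Secondary Outcomes that will be compared between groups include": FSFI, I-QOL, perception of monetary value, QUID, and two visual analog scales (patient discomfort and procedure difficulty).

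The Research Visit Summary lists FSFI, I-QOL and QUID at the baseline visit under "Three surveys before the procedure", ahead of the blood draw and randomization. The follow-up text under Injection Procedure says "At baseline and at time points of 3 and 6 months, all validated questionnaires will be completed". The visit list adds I-QOL and QUID at the 1-month telephone call.

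The other three have no baseline value. The two scales are completed once, just after the injection: "the patient will be given the VAS for pain/discomfort related to the procedure and the injector will complete the VAS for procedure difficulty". Perception of monetary value appears only at the 6-month visit.

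Statistical Analysis and Data Reporting gives two analyses for secondary outcomes. One is "Primary and secondary outcomes will also be compared using treatment-stratified summary statistics, and p-values obtained using the aforementioned statistical tests", which for scores means "T-test or Wilcoxon rank sum tests for continuous variables, where appropriate". The other is "Univariate generalized linear models using treatment group as the predictor variable will also be examined for the secondary outcomes". A model with further covariates is planned for the primary outcomes only. Nothing names the response for the questionnaires (follow-up score or change) or the visit at which they are compared.

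**The concern.** The baseline score of a questionnaire is often the best available predictor of its later score. Leaving it out of the model leaves avoidable noise in the treatment comparison, and with about 20 completers per arm precision is already limited. Using the change score is only a partial answer: it beats the follow-up score when the correlation is above 0.5 and is worse below it, and the correlation is not known in advance.

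The open definition is a second cost. I-QOL and QUID each allow 3 visits × 2 responses × 2 tests = 12 comparisons, and FSFI allows 2 × 2 × 2 = 8. That makes 12 + 12 + 8 = 32 possible results for three outcomes, with none designated as the one to report.

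Bias is not at stake. Randomization makes the unadjusted comparison valid, and a chance baseline difference is part of the same sampling variability, not an additional error.

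**Working it through.** **The plan's own figure.** The only sample size concerns the binary primary outcome, "assuming true response rates of 70% and 20% for treatment and placebo groups, respectively". With two-sided alpha 0.05, 90% power and pooled variance under the null, n per arm = [1.960·√(2·0.45·0.55) + 1.282·√(0.21 + 0.16)]² / 0.50² = 18.6, so 19. This reproduces the stated 38 in total. It says nothing about the questionnaires, for which no power is given.

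**Inputs.** Completers: 50 × 0.8 = 40, or n = 20 per arm (Power Analysis; the Timetable section also gives 40). Alpha is 0.05, taken as two-sided. Assumed, because the documents are silent: correlation ρ between baseline and 6-month score, equal SDs at the two visits, and illustrative effects of 0.6 and 0.8 SD.

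**Variance of the treatment difference, in SD² units.**
- Follow-up score: 2/n = 0.100 (38 df)
- Change score: 2(1 − ρ)·2/n (38 df)
- Baseline-adjusted (ANCOVA): (1 − ρ²)·(2/n)·(1 + 1/36) (37 df)

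| | ρ = 0.3 | ρ = 0.5 | ρ = 0.7 |
|---|---|---|---|
| Follow-up | 0.100 | 0.100 | 0.100 |
| Change | 0.140 | 0.100 | 0.060 |
| ANCOVA | 0.0935 | 0.0771 | 0.0524 |
| Cut against the better unadjusted choice | 6.5% | 22.9% | 12.6% |
| Equivalent extra patients | 6.9% | 29.7% | 14.5% |
| 95% CI half-width, better unadjusted to ANCOVA (SD) | 0.64 to 0.62 | 0.64 to 0.56 | 0.50 to 0.46 |
| Power, 0.6 SD | 46 to 48% | 46 to 56% | 67 to 72% |
| Power, 0.8 SD | 69 to 72% | 69 to 80% | 89 to 93% |

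Power is from the noncentral t. The gain peaks near ρ = 0.5; it is 1.3% at 0.2 and 7.5% at 0.8.

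**Cost of the wrong unadjusted choice.** At ρ = 0.3, ANCOVA has 1 − 0.0935/0.140 = 33% less variance than the change score. At ρ = 0.7 it has 1 − 0.0524/0.100 = 48% less than the follow-up score.

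**Where it does not help.** ANCOVA matches the follow-up score when (1 − ρ²)(37/36) = 1, that is ρ = √(1/37) = 0.164. Below that it loses at most about 1.3 points of power.

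**Stress test with the plan's 70% and 20% response rates.** Suppose only responders shift, by s SD (assumed). The average extra within-arm variance is m = s²·(0.21 + 0.16)/2 = 0.185s². The relative variances become 1 + m (follow-up), 2(1 − ρ) + m (change) and (1 − ρ² + m)(37/36) (ANCOVA).
- s = 1.2, m = 0.266: ANCOVA 1.209 / 1.045 / 0.798 against 1.266 / 1.266 / 0.866, a cut of 4.5% / 17.5% / 7.9%.
- s = 2, m = 0.74: ANCOVA 1.696 / 1.531 / 1.285 against 1.740 / 1.740 / 1.340, a cut of 2.5% / 12.0% / 4.1%.

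The break-even ρ rises to √(1.266/37) = 0.19 and √(1.74/37) = 0.22.

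**Simulation (20,000 trials per setting).** The comparator is the best of t-test or Wilcoxon on follow-up or change.

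| Setting | ANCOVA power, ρ = 0.3 / 0.5 / 0.7 | Best unadjusted |
|---|---|---|
| Responders shift 1.2 SD | 39.4 / 45.0 / 54.4% | 37.8 / 38.3 / 51.7% |
| Responders shift 2 SD | 65.0 / 68.9 / 75.9% | 64.9 / 64.9 / 74.4% |
| Scores bounded at about −1.0 and +1.2 SD, 0.6 SD effect | 44.9 / 50.4 / 64.2% | 42.8 / 42.5 / 56.4% |

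ANCOVA type I error was 4.8 to 5.1% in every null setting, including the bounded scores.

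**The case against.** An unadjusted comparison in a 1:1 randomized trial is a legitimate choice, and no sample size or success criterion rests on these questionnaires. The correlation is not in the documents, so no particular loss can be demonstrated for this trial. Under the plan's own response rates with a 2 SD responder shift, the power gain is only about 0, 4 and 1.5 points. The visit is also less open than it seems, because the stated aim is efficacy at 6 months. Finally, a baseline covariate does not settle how scores from women who leave early for other treatment, or missing baselines, are handled.

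Most of this stands as a limit on size. The point concerns efficiency and definition on secondary outcomes, and the gain could be small. It does not defeat the recommendation: adjustment is best, or within about 1.3 power points of best, across the range examined, whereas either unadjusted choice can be clearly the wrong one. A 6-month aim still leaves follow-up score or change undecided. Early-exit scores and missing baselines need a rule, but they arise equally under the unadjusted analysis.

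**Conclusion.** The concern holds. The plan collects pre-randomization scores for three secondary outcomes, uses none of them in the comparison and leaves the response undefined. With 20 completers per arm, equal SDs and ρ between 0.3 and 0.7, baseline adjustment cuts variance by about 6 to 23% against the better unadjusted choice when all women share one effect. The cut is roughly 2 to 18% when only some respond. The omission is certain from the text; the size depends on the assumed correlation and effect pattern. The change should be made, but nothing in the primary analysis or sample size depends on it.

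**What to change.** For each of FSFI, I-QOL and QUID, replace the treatment-only model with a linear model of the 6-month score on treatment and the same questionnaire's baseline score. Report the adjusted mean difference with its 95% CI. Use the same model at 3 months, and at 1 month for I-QOL and QUID, as supportive. Keep the unadjusted follow-up comparison (t-test, or Wilcoxon where scores are skewed) as a sensitivity analysis. Leave the two visual analog scales and perception of monetary value unadjusted, because they have no baseline.

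The cost is two or three sentences naming response, visit and covariate, written before the data are seen. Each model spends one degree of freedom, worth at most about 1.3 points of power against the follow-up score if the correlation is near zero. No new data or visits are needed.
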